8.3 Endpoint Analysis Details

A. Preliminary calculations

a. Calculate mock-adjusted T cell responses for all participants at baseline (prevaccination) and Days 35, 42, and 56.

- i. (arithmetic mean antigen wells arithmetic mean mock), averaged across replicates.
- ii. Report mock adjusted antigen response as spot-forming units (SFU) per 10⁶ PBMC, typically extrapolated from an input cell number of 0.2M PBMC/well.
- iii. Calculations require a minimum of 3 mock replicates.
- iv. Calculations require a minimum of 2 antigen replicate wells.

Note I: Lower replicate numbers arise from i) insufficient cells or ii) well failure, mostly due to membrane issues.

Note II: The PHA positive control is a QC assessment at the laboratory level. Only passing data will be submitted for analysis (see also Table 1).

b. Define and report ex vivo positive/reactive T responses to antigen pools at each timepoint per participant:

- i. Calculate ex vivo mock-adjusted T cell response with the following additional criteria:
 - Average (arithmetic) of ex vivo mock-adjusted replicate wells > 20
 SFU/10⁶ PBMCs. Otherwise, assign a value of 20 SFU/10⁶ PBMCs.
 - Average (arithmetic) of ex vivo antigen replicate wells (not mockadjusted) is ≥ four times the average (arithmetic) of mock wells.
 Otherwise, assign a value of 20 SFU/10⁶ PBMCs.
 - 3. Zero values are not accepted in any ex vivo replicate of antigenstimulated wells. Otherwise, assign a value of 20 SFU/10⁶ PBMCs.
 - For example, if replicates in peptide pool PP062 wells are 40, 0, 34, 10 and the average was 21 SFU/10⁶, this would not be designated a positive/reactive response because of lack of certainty.
 - 5. Summarize reactivity data per individual and per treatment arm.

- B. Calculate fold-change in ex vivo ELISpot response to both vaccine and non-vaccine immunogens (Outcome 1 T-Cell Magnitude):
 - a. Analysis criteria:
 - i. The change in ex vivo ELISpot response will be examined using the log2 fold change of the quantified ELISpot response between the average of baseline visits and Day 35 and Day 42.
 - ii. No submitted data are to be excluded for fold-change analysis.
 - iii. All mock-adjusted averages (arithmetic) < 20 SFU/10⁶ PBMCs or that do not meet the criteria of a 'positive/reactive' T cell response (described in C) will be assigned a value of 20 SFU/10⁶ PBMCs.
 - b. Secondary analysis within vaccine arms (n=8/group):
 - i. Report results as log2 fold change to each antigen pool (Mos-1/PP062, Mos-2/PP063, Subpools PP076-080) for each vaccine arm.
 - ii. All log2 fold changes will be statistically assessed using a two-sided exact Wilcoxon signed-rank test. If a value in the dataset matches the hypothetical value, then the value will be ignored in the analysis (Wilcoxon method of handling ties).
 - c. Secondary analyses between vaccine arms (n=8/group):
 - i. Examine the between-arm difference in log2 fold change to each antigen pool Mos-1/PP062 and Mos-2/PP063 pre- and post-vaccination.
 - ii. Between-arm comparisons in log2 fold changes will be statistically assessed using a two-sided exact Wilcoxon rank-sum test. If a value in the

dataset matches the hypothetical value, then the value will be ignored in the analysis (Wilcoxon method of handling ties).

C. Calculate gain or loss of a positive T cell responses to vaccine immunogens to assess breadth (Outcome 2 T-Cell Breadth):

- a. To analyze breadth, we are looking at the number of reactive subpools before (screening, enrollment, Day 0) and after vaccination (Day 56).
- b. As per section 8.3.A.b, assess whether ex vivo T cell response is reactive/positive at each visit.

c. Analysis criteria:

- i. For breadth analysis, output should be binary: non-response or response
- ii. No. of positive HIV subpools 1-5 (PP076-PP080) pre-vaccination at baseline.
- iii. Pre-vaccination breadth: if a reactive/positive T cell response is observed at *any* pre-vaccination visit that the participant will be deemed to have a positive/reactive T cell response pre-vaccination.
- iv. No. of positive antigen subpools 1-5 (PP076-PP080) post-vaccination.
 - Post vaccination breadth: ex vivo vaccine-induced T cell response must be detected at > 1 post-vaccination visit, Day 35 onward.
- v. Data was only submitted for analysis if it met biological criteria.
- d. Secondary analysis across all vaccinees (n=16) & within arm (n=8/group):
 - i. Change in number of positive HIV subpools (PP076-80) at Day 56 (post-vaccination) vs baseline (pre-vaccination) across all vaccinees (n=16).
 - ii. Change in number of positive/reactive HIV subpools (PP076-80) at Day 56 (post-vaccination) vs baseline (pre-vaccination) for each vaccine arm.
 - iii. The change in number of positive/reactive antigen subpools will be statistically assessed using a two-sided exact Wilcoxon signed-rank test. If

a value in the dataset matches the hypothetical value, then the value will be ignored in the analysis (Wilcoxon method of handling ties).

- e. Secondary analysis between vaccine arms (n=8/group):
 - Compare the change in number of positive/reactive antigen subpools at Day 56 vs baseline for study arm C1C62-M3M4 to the change in number of positive/reactive antigen subpools at Day 56 vs baseline for study arm C62-M4.
 - ii. Between-arm comparisons in breadth will be statistically assessed using a two-sided exact Wilcoxon rank-sum test. If a value in the dataset matches the hypothetical value, then the value will be ignored in the analysis (Wilcoxon method of handling ties).

9 Interim Analyses

During the SMC annual meeting and Closed Session Reports, the SMC will discuss the primary endpoint, participant safety through Day 28 following second vaccination with M3M4 or M4. This assessment will serve as a basis for allowing enrollment to continue and, at the request of the SMC, the statistician may be present during the closed session.

Safety Pause meetings will be called if:

- a) Two or more participants experience a primary safety outcome measure that is a
 Grade ≥3 AE possibly related to study treatment (as judged by the core team, blinded to treatment arm); or
- b) One or more participants experience an SAE possibly related to study treatment (as judged by the core team, blinded to treatment arm).

This "ad hoc" report, typically prepared by the statistician or data manager, will include the relation of the AE or SAE to study treatment thought by the blinded core team to be a primary safety outcome. Following the review, the SMC will recommend if and how the

study should proceed with respect to resuming enrollment and continuing study treatment. To the extent possible, decisions regarding additions or modifications to planned analyses, inclusion/exclusion from analysis cohorts, and handling of missing or incomplete data will be made by the statisticians or other study staff prior to review of arm-specific results.

10 ELISPOT Data

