1.2 Schema

1.3 Schedule of Activities (SoA)

16.1.1 Protocol

IGHID-12107 - The CM (HIV-CORE 008) Study Version 3.0

ChAdOx1.HIVcons62 (C62) boosted with MVA.tHIVcons4 (M4) or C62+

ChAdOx1.tHIVcons1 boosted with M4+MVA.tHIVcons3 (M3)

Confidential

Page 18 of 143

	Screening	Enrollment and Baseline	Day 0 Vaccination	Day 2	Day 7	Day 14	Day 28 Vaccine Booster	Day 30	Day 35	Day 42	Day 56	Day 84	Day 140	Day 196 EOS
CMV and EBV Test		X												
COVID-19 Antibody Test		X ⁵	X ⁵		X ⁵	X ⁵	X ⁵		X ⁵	X ⁵	X ⁵		X ⁵	
Plasma and PBMC for Immunologic and Virologic Studies	X	X ⁶	X		X	X	X		X	X	X	X ⁷	X	X

Table Legend¹ See [Appendix 2](#) detailing additional telephone assessments at Days 5, 10, 18 and 22.² Leukapheresis should be scheduled as close to the screening visit as feasible.³ See Section 8.1.2.⁴ Collect and store sample at enrollment. All other testing (if required) will be performed in real time.⁵ Test only retrospectively from stored plasma if immune response data suggest need.⁶ Collect separate research PBMCs samples at Enrollment.⁷ Collect sample only if participant completed Day 56 leukapheresis. If participant completed large blood draw instead of leukapheresis, do not collect sample.

AE=adverse events; AESI = AE of special interest; EOS = end of study; MAAE = medically attended AE;

PE=physical exam; PID=participant ID; POCT=point of care test; RID=randomization ID; SAE=serious AE; SID=study ID; WOCBP=woman of childbearing potential

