5.3 Power Calculations for Secondary Endpoints

Table 4 and Table 5 provide power calculations for both immunogenicity secondary endpoints. For the first of the secondary endpoints, the outcome will be the HIV-specific T cell response to peptides spanning either the Mos-1 (PP062) or Mos-2 (PP063) immunogens at baseline visits, Day 35, and Day 42 (following C62-M4 or C1C62-M3M4 vaccination). For the within arm calculation, an average fold change of at least 2 (comparing T-cell responses within participants) is anticipated to be scientifically meaningful. For the between arm calculation, a relative change that is greater for any given participant in the C1C62-M3M4 arm than in the C62-M4 arms alone is anticipated to be scientifically meaningful if it occurs at least 90% of the time.

For the second of the secondary endpoints, the outcome will be breadth of T-cells targeting peptide subpools (n=5 subpools PP076, PP077, PP078, PP079, PP080) spanning the conserved immunogens of HIV-1. HIV-specific T-cell responses will be measured at pre-vaccination visits (1-3 visits/participant) and at post-vaccination (Day 56).

Table 4: Power for detecting differences in T-cell magnitude.

| Within Arms | Between Arms (C1C62-M3M4 vs C62-M4) |
|--|---|
| Aim: Determine the statistical power necessary to detect a geometric mean ratio (GMR) of 2 for the within-participant HIV-specific T-cell response. | Aim: Assuming identical distributions of differences in both arms (i.e. assuming a location-shift-only alternative), determine the statistical power necessary to compare median differences in HIV-specific T-cell responses. |
| Data: Assume normally distributed natural, log-transformed, HIV-specific T cell responses from | Data: Assume normally distributed differences in HIV specific T-cell response |

pre-vaccination (one or more of screening, enrolment, pre-vaccination leuk, Day 0) and postvaccination (Day 35 and 42) for all arms. between pre-vaccination (screening, enrolment, pre-vaccination leuk, Day 0) and post-vaccination (Day 35 and 42) for vaccine arms.

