relative change within participants will be estimated using a geometric mean ratio (GMR, also known as fold change) and evaluated with an exact two-sided Wilcoxon signed-rank test for within-arm comparisons and an exact two-sided Wilcoxon rank-sum test for between-arm comparisons. The Wilcoxon signed-rank test assumes symmetry of the change in natural log-transformed summed HIV-1 specific T cell response (estimated by GMR) under the null. If this assumption is violated, then a sign test will be conducted as a sensitivity analysis.

Outcome 2 (T-Cell Breadth): Change in breadth (difference in the number of ex vivo reactive/positive P076, PP077, PP078, PP079, PP080 subpools pre- and post-vaccination) of T-cell responses targeting HIV-conserved regions from pre-vaccination (one or more of screening, enrolment, pre-vaccination leuk, Day 0) to post-vaccination (Day 56).

This outcome consists of the following two components:

Outcome 2.1: Change in breadth of T-cell responses from pre-vaccination to post-vaccination (Day 56) within vaccinated arm.

Outcome 2.2: Comparison of change in breadth of T-cell responses from pre-vaccination to post-vaccination (Day 56) between vaccinated arms.

Analysis: Breadth is measured as the number of ex vivo reactive subpools (P076, PP077, PP078, PP079, PP080). To evaluate change in breadth in the number of T cell responses targeting HIV-conserved regions from baseline (pre-vaccination) to post-vaccination (D56), an exact two-sided Wilcoxon signed-rank test will be used for within-arm comparisons and an exact two-sided Wilcoxon rank-sum test will be used for between-arm comparisons.

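### T-cell breadth is scored by a looser rule before vaccination than after, on visits the SAP does not fix, so the within-arm and pooled tests are biased even with no vaccine effect

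*SAP*

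**What the plan says.** Breadth is the number of reactive subpools out of five (PP076 to PP080), and the outcome is the count after vaccination minus the count before. SAP 8.3.C.c gives two rules:

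- **Before** (item iii): positive "if a reactive/positive T cell response is observed at *any* pre-vaccination visit".
- **After** (item iv): "ex vivo vaccine-induced T cell response must be detected at > 1 post-vaccination visit, Day 35 onward".

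The visits behind each rule differ from place to place:

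- **Pre-vaccination.** SAP 5.3 allows one to three visits per participant. SAP 8.3.C.a names screening, enrolment and Day 0. SAP 8.2 accepts one or more of four samples, adding the leukapheresis. SAP 4.2 has a further general rule that averages all measures up to randomization.
- **Post-vaccination.** Outcome 2.1 in SAP 8.2 reads "Change in breadth of T-cell responses from pre-vaccination to post-vaccination (Day 56) within vaccinated arm", and SAP 5.3 and 8.3.C.a also name Day 56 only. SAP 8.3.A.a says "Calculate mock-adjusted T cell responses for all participants at baseline (prevaccination) and Days 35, 42, and 56". Item iv has no last visit. The Protocol 1.3 row "Plasma and PBMC for Immunologic and Virologic Studies" has collections at Days 35, 42, 56, 84 (conditional), 140 and 196.

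The change goes into exact two-sided signed-rank tests within each arm and across all 16 vaccinees, with zero changes dropped. The between-arm comparison (Outcome 2.2) uses an exact rank-sum test.

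**The concern.** A signed-rank test against zero is valid only if the change is centred on zero when nothing has happened. Here the baseline gets the benefit of any single positive call, while the follow-up must be confirmed. A subpool near the positivity cutoff will tend to count before and not after, which looks like a loss.

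The text also cannot be carried out as written, because a Day 56 count from one visit can never satisfy a requirement for more than one visit. Whoever runs the analysis must choose the visits, and that choice sets both the size and the direction of the bias. At stake are Outcome 2.1 and the pooled test: a true gain may be missed, a loss declared that did not occur, or, with few baseline and many follow-up visits, a gain declared that is only scoring.

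**Working it through.** **Stated figure.** The only operating characteristic given for breadth is 95% between-arm power (SAP Table 5; Protocol 10.7.4.4). Simulating the two stated change distributions with n=8 per arm and the exact rank-sum test gives 95.4%, so that figure reproduces. Nothing is stated for the within-arm or pooled tests.

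**Assumptions.** Rules are applied to each subpool, with per-visit positivity q the same before and after (no vaccine effect) and visits independent given q. The documents do not give q, so a range is used.

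**Expected change per subpool**, post = more than one of Days 35, 42, 56:

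- P(post+) = 3q^2 - 2q^3
- P(pre+) = 1 - (1-q)^k for k pre-vaccination visits
- k=3: change = -3q(1-q)^2
- k=2: change = -2q(1-q)^2
- k=1: change = -q(1-q)(1-2q)

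For k=3 and q=0.5 this is -3 × 0.5 × 0.25 = -0.375 per subpool, or -1.875 over five.

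| Sum over five subpools | q=0.1 | q=0.5 | q=0.9 |
|---|---|---|---|
| 3 pre visits | -1.2 | -1.9 | -0.1 |
| 2 pre visits | -0.8 | -1.25 | -0.1 |
| 1 pre visit | -0.4 | 0 | +0.4 |

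**Null rejection of the exact signed-rank test**, zeros dropped as the SAP states (10,000 simulated arms for n=8; 4,000 for n=16). The second column is -3 times the sum of q(1-q)^2; the other columns are percentages.

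| q of the five subpools | Mean change, 3 pre/3 post | n=8, 3 pre/3 post | n=8, 2/3 | n=8, 1/3 | n=8, 1/6 (false gain) | n=16, 3/3 |
|---|---|---|---|---|---|---|
| .95 .95 .5 .05 .05 | -0.66 | 21.2 | 7.5 | 0.6 | 9.4 | 80 |
| .9 .9 .5 .1 .1 | -0.92 | 39.4 | 14.1 | 0.9 | 14.6 | 94 |
| .9 .5 .5 .1 .1 | -1.26 | 59.5 | 24.6 | 1.2 | 32.1 | 98 |
| .98 .98 .3 .02 .02 | -0.56 | 19.2 | 5.6 | 0.3 | 3.3 | 68 |
| .95 .95 .95 .05 .05 | -0.29 | 0.7 | 0.2 | 0.0 | 0.0 | 24 |
| .99 .99 .02 .02 .02 (stable) | -0.17 | 0.1 | 0.0 | 0.0 | 0.0 | 3 |

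With three pre and six post visits, rejection is 2.4% or less. If follow-up is Day 56 alone against any of three pre visits, it is 0% to 48% at n=8.

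**Masking (n=8).** One subpool rises from q=0.1 to 0.9 and the others stay at .9, .9, .5, .1. A gain is declared in 38%, 4% and 0.5% of arms with 1, 2 and 3 pre visits, against 49% with at least 2 of 3 on both sides. With stable subpools (others .99, .99, .02, .02; rise from .02 to .99) the figures are 98%, 91% and 82%, against 100%.

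**Meaning of vaccine-induced (3 pre visits, n=8).** If confirmation applies only to new responses, null rejection is 0% to 5.5% when a baseline-positive subpool is kept on any positive from Day 35 to Day 56. It is 0.1% to 61% when the subpool must be positive at Day 56.

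**Between-arm test.** Null rejection is 0.2% to 3.2%, because both arms carry the same scoring bias.

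**The case against.** The best case for the plan has five parts.

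- **Scope.** The stated breadth hypothesis is between arms (Protocol 10.1), and that test is not inflated. This stands, and the concern is limited accordingly. But within-arm breadth is Outcome 2.1 and is planned in Protocol 10.7.4.3, and the pooled test is listed as a secondary analysis.
- **Direction.** With Days 35, 42 and 56 after vaccination, almost all errors are false losses; false gains are 0.4% or less at n=8. Asking for confirmation of a new response is a defensible, conservative choice. That holds for claiming a gain, but the cost is masking, and the test is two-sided.
- **Stability.** Protocol 4.2 describes T cell responses under durable suppression as very stable, and the stable pattern stays below 5% in both tests. This is the main limit on size. However, the statement concerns responses in general. Subpool calls depend on a 20 SFU cutoff, a fourfold-mock rule and a no-zero-replicate rule, and nothing shows that these calls are stable.
- **Larger effects.** If two subpools rise from 0.1 to 0.9 (others .9, .9, .5), power is 97%, 72% and 47% with 1, 2 and 3 pre visits. Masking is less severe than in the one-subpool example, but with three pre visits it is still 47% against 99% under a matched rule.
- **Visit choice.** The false-gain case needs one baseline visit for everyone and use of all samples to Day 196, while SAP 8.3.A.a computes responses only to Day 56. It is the less likely reading, but item iv leaves it open.

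If the more-than-one sign is a conversion error for at least one, unequal visit numbers still bias the change. One pre visit against any of three post visits at q=0.2 gives +1.4 subpools and false gains in 51% of arms.

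**Conclusion.** The concern holds. The two rules are unequal as written, the post-vaccination rule contradicts the Day 56 definition, and the visits are not fixed. With three visits per side the change is biased downward for every q strictly between 0 and 1.

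The size depends on q, which the documents do not give, and on independence of visits given q. It runs from negligible when calls are nearly all stable to severe when one or two of five subpools sit near the cutoff, and the pooled test is hit hardest. Confidence is high that the rule is wrong as written and conditional on q for how much it matters. It should be fixed, as it affects secondary within-arm and pooled inference, not the primary safety endpoint. No loss of power was quantified for the between-arm test.

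**What to change.** Use one positivity rule, named visits and the same number of visits on both sides. Two workable forms:

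1. Positive in at least 2 of screening, enrolment and Day 0, against at least 2 of Days 35, 42 and 56. Null mean change is 0; rejection at n=8 is 1.0% or less over the same six patterns.
2. The Day 56 count against the average per-visit pre-vaccination count. Null mean change is 0; rejection is 3.2% or less.

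Also:

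- State whether vaccine-induced restricts confirmation to new responses, and how a baseline-positive subpool is kept.
- Set a fallback for participants with fewer than three pre-vaccination samples, such as Day 0 against Day 56 (null mean 0; rejection 1.3% or less if used for all).
- Reconcile the rule with the averaging in SAP 4.2.
- Fix all this before arm-specific results are seen, and keep the current rule, with its visits named, as a sensitivity analysis.

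**Cost.** SAP wording and no new visits, since the schedule already collects PBMC at all six named visits, though assays must be available there. Form 1 needs three evaluable samples per side, may leave some baseline samples unused, and must be squared with the Day 56 endpoint in Protocol Sections 3 and 10.2. Form 2 keeps Day 56, but a single call is noisier than a confirmed one, its difference from an average is not exactly symmetric under the null, and the averaged baseline must be squared with the binary output in SAP 8.3.C.c.i.

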10.7.4.3 T cell Breadth

To evaluate change in breadth in the number of T cell responses targeting HIV-conserved regions from baseline (pre-vaccination) to post-vaccination (D56), an exact two-sided Wilcoxon signed-rank test will be used for within-arm comparisons and an exact two-sided Wilcoxon rank-sum test will be used for between-arm comparisons.

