10.7.4.4 Power Calculations for T cell Breath

Baseline HIV-specific T cell breadth from durably-suppressed PWH were used to inform power calculations (50). In this study, reactive HIV T cell epitopes in the HIV proteome (Clade B consensus and autologous reservoir virus) were defined in 25 PWH on ART.

For the **C62-M4** and **C1C62-M3M4** arms, we anticipate that vaccination will induce a change of breadth (the detection of a new reactive T cell epitope) ranging from 0-3 epitopes and 2-6 epitopes, respectively.

- We anticipate that **C62-M4** will induce a change in breadth with the following frequency distribution: 0 (20% of participants), 1 (50%), 2 (20%), and 3 (10%).
- We anticipate that **C1C62-M3M4** will induce a change in breadth with the following frequency distribution: 2 (30% of participants), 3 (40%), 4 (15%), 5 (10%), and 6 (5%).

Given these assumptions, n=8 evaluable participants per treatment arm provides 95% power to detect a difference between arms using an exact two-sided Wilcoxon rank-sum test (at a 0.05 significance level).

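### SAP 8.3 attaches the signed-rank rule for dropping zeros to the between-arm rank-sum tests; read as zero change, it cuts planned breadth power from 95.5% to 86.4%

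*SAP*

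**What the plan says.** SAP 8.3 has four test items. Two are within-arm signed-rank tests (8.3.B.b.ii for magnitude, 8.3.C.d.iii for breadth). The magnitude item begins: "All log2 fold changes will be statistically assessed using a two-sided exact Wilcoxon signed-rank test". Two are between-arm rank-sum tests (8.3.B.c.ii and 8.3.C.e.ii). The magnitude item begins: "Between-arm comparisons in log2 fold changes will be statistically assessed using a two-sided exact Wilcoxon rank-sum test". All four end with the same rule, labelled as Wilcoxon's method for ties. For the between-arm breadth test the text runs "assessed using a two-sided exact Wilcoxon rank-sum test. If a value in the dataset matches the hypothetical value, then the value will be ignored".

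Other places that bear on the point:

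- The heading of 8.3.C.e reads "Secondary analysis between vaccine arms (n=8/group)", so all 8 per arm are expected in the test.
- SAP 8.2 defines the endpoint: "Breadth is measured as the number of ex vivo reactive subpools". There are five subpools.
- Protocol 10.7.4.3 says an "exact two-sided Wilcoxon rank-sum test will be used for between-arm comparisons". Like SAP 8.2, it mentions no deletion and does not discuss zeros.
- Protocol 10.7.4.4 states that "n=8 evaluable participants per treatment arm provides 95% power to detect a difference between arms using an exact two-sided Wilcoxon rank-sum test".
- SAP 8.3.B.a.ii says that no submitted data are left out of the fold-change analysis.

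**The concern.** The signed-rank test ranks the absolute differences from a hypothesised value, here zero change, so a rule for differences of exactly zero is needed. The rank-sum test ranks the two arms together and compares no observation with a fixed value. A participant with zero change is an ordinary low observation, and ties between participants are handled by midranks. The repeated sentence has nothing to act on unless the analyst carries zero over from the signed-rank item just above it, which uses the same change scores.

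If that is done, valid participants are removed because of a post-randomisation outcome. For breadth, a zero need not even mean non-response: new responses that fall in subpools already reactive at baseline also give zero change. The between-arm breadth test addresses the study's second hypothesis, that the bivalent regimen gives the greater breadth. Removing the lowest values from the arm expected to do worse narrows the contrast and biases toward no difference. Two analysts who read the sentence differently could report different p-values from the same 16 participants.

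**Working it through.** **Inputs.** There are 8 participants per arm and a two-sided alpha of 0.05 (SAP 4.1.8). The planned changes in breadth come from protocol 10.7.4.4 and the Data row of SAP Table 5:

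| Change | 0 | 1 | 2 | 3 | 4 | 5 | 6 |
|---|---|---|---|---|---|---|---|
| C62-M4 | 20% | 50% | 20% | 10% | – | – | – |
| C1C62-M3M4 | – | – | 30% | 40% | 15% | 10% | 5% |

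**Method.** Every possible multinomial outcome in one arm was crossed with every outcome in the other, so there is no simulation error. For each pair, W is the midrank sum in C62-M4 and μ = n₁(N+1)/2. The p-value is the share of all allocations of the observed values to the arms with |W − μ| at least as large as observed. Power is the total probability of pairs with p < 0.05.

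**Step 1: reproduce the plan.** With all 16 kept, power is 95.5%, against the stated 95%.

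**Step 2: apply the sentence as zero change.** Power is 86.4%, a loss of 95.5 − 86.4 = 9.1 points. If the two-sided p is taken as twice the smaller tail, the figures are 95.5% and 84.5%. Capping change at 5, the number of subpools, leaves the main figures at 95.5% and 86.4%.

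**Step 3: who is removed.**

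- Expected number dropped from C62-M4: 8 × 0.20 = 1.6. From C1C62-M3M4: 0.
- P(at least 1 dropped) = 1 − 0.8⁸ = 0.832.
- P(at least 2 dropped) = 1 − 0.8⁸ − 8 × 0.2 × 0.8⁷ = 1 − 0.168 − 0.336, about 0.50.
- C62-M4 mean change: 0.5 + 0.4 + 0.3 = 1.2 kept, and 1.2/0.8 = 1.5 dropped.
- C1C62-M3M4 mean change: 0.6 + 1.2 + 0.6 + 0.5 + 0.3 = 3.2.
- Mean difference: 3.2 − 1.2 = 2.0 kept, and 3.2 − 1.5 = 1.7 dropped.

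**Step 4: type I error.** With both arms given the C62-M4 distribution, it is 2.8% kept and 1.8% dropped.

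**Step 5: subpool scale (illustration).** The planning distributions count individual epitopes, but the endpoint counts reactive subpools. Assume that each epitope falls in one of the five subpools in proportion to its peptide count in SAP Table 1 (64, 38, 42, 54, 41; total 239), independently, and that no response is lost. Change is then the number of newly reactive subpools. For one baseline epitope and subpool weights w, the zero rate in C62-M4 is 0.20 + 0.50Σw² + 0.20Σw³ + 0.10Σw⁴. With Σw² = 0.208, Σw³ = 0.045 and Σw⁴ = 0.010 this is 0.31.

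| Baseline epitopes (assumed) | Zero rate, C62-M4 | Zero rate, C1C62-M3M4 | Power, zeros kept | Power, zeros dropped |
|---|---|---|---|---|
| 0 | 20% | 0% | 84% | 68% |
| 1 | 31% | 2% | 64% | 31% |
| 3 (mean in protocol 2.2.3.1) | 52% | 16% | 32% | 3% |
| Uniform on 0–6 | 49% | 19% | 29% | 6% |

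Only the gap between the last two columns belongs to this point. The fall down the zeros-kept column comes from the change of scale and the assumed baseline.

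**Magnitude.** Responses below 20 SFU or not positive are set to 20 (SAP 8.3.B.a.iii). A participant at that floor both before and after vaccination has a log2 fold change of exactly zero. The documents give no rate for this, so no size is computed.

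**The case against.** The strongest reply is that the plan shows elsewhere that zeros are meant to stay. The stated 95% matches the planning distributions only with zeros kept. The headings assume 8 per group. The Design row of SAP Table 5 describes the same rank-sum test against a C62-M4 arm with no change at all; under deletion that arm would be empty and no test could be run. For magnitude, 8.3.B.a.ii forbids excluding submitted data. The analyst would also have to supply a value that the SAP never gives for this test.

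This makes the deletion reading less likely, but it is inference from planning text and headings. The sentence in the test specification still instructs that values be ignored. The conflict with 8.3.B.a.ii is itself a reason to clarify.

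Three further limits stand. The 9.1-point loss is conditional and rests on epitope counts. The subpool figures rest on assumptions, including that no response is lost. SAP 8.3.C.c counts baseline reactivity at any pre-vaccination visit but asks for more than one post-vaccination visit, so negative changes can occur; the direction of the effect was shown only for non-negative changes. Finally, this is a secondary endpoint in a Phase 1 study whose protocol (10.7.1) puts the emphasis on description and effect sizes, and the primary safety analysis is untouched.

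**Conclusion.** The concern holds. A one-sample rule is written into two two-sample tests where it has no defined meaning, so the text is wrong as it stands whichever way it is read. If it is inert, nothing is lost by removing it. If it is applied as zero change, between-arm breadth power on the plan's own distributions falls from 95.5% to 86.4%, with an 83% chance of losing at least one C62-M4 participant. That size assumes the deletion reading and that the epitope-based distributions carry over to subpools; on the subpool scale the loss could be larger, depending on baseline reactivity. Type I error is not inflated, and no size is claimed for magnitude. The SAP should be corrected, but the error does not threaten the trial's primary conclusion.

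**What to change.** - Delete the sentence on the hypothetical value from SAP 8.3.B.c.ii and 8.3.C.e.ii.
- State in both items that all evaluable participants, including those with zero change, enter the rank-sum test, with ties given midranks and the p-value taken from the exact conditional (permutation) distribution.
- Keep the zero rule in the signed-rank items (8.3.B.b.ii and 8.3.C.d.iii), name zero change as the value, and add that 8.3.B.a.ii does not bar it there.
- As a separate correction, reconcile the two rows of SAP Table 5. The Design row takes no change in any C62-M4 participant, which fully separates the arms and gives 100% power with zeros kept. The stated 95% comes from the Data row.

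The cost is one sentence removed in two places and a few words of clarification, with no new data and no change to trial conduct. SAP section 9 wants choices of this kind settled, as far as possible, before anyone looks at the data by arm: "inclusion/exclusion from analysis cohorts, and handling of missing or incomplete data will be made by the statisticians or other study staff prior to review". SAP section 1 provides a revision history for such changes. SAP 10.1 already describes the assays in the past tense, so the edit should be made and dated promptly.
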